**Statistical Analysis Plan**

Sponsor: Zogenix International Limited; Protocol No.: ZX008 Study 2 (ZX008-1501 and ZX008-1502)

ZX008 0.2 mg/kg/day	Placebo	Placebo
ZX008 0.8 mg/kg/day	ZX008 0.4 mg/kg/day	ZX008 0.2 mg/kg/day
Placebo	Placebo	Placebo
Note: maximum daily dose of ZX008 is 30 mg.		

**Transition Period:**

Subjects who completed the Maintenance Period and were continuing into the open-label extension study were to be transitioned from double-blind study medication to open-label ZX008 (Table 3). Study medication was administered as equal doses BID in the morning and in the evening approximately 12 hours apart, with food. Each dose should have been separated by a minimum of 8 hours and a maximum of 12 hours. A missed dose of study medication may have been taken later up to 8 hours before the next scheduled dose; otherwise, the missed dose should not be given. Study medication was administered using the oral dosing syringe provided.

All subjects entering the open-label extension study were transitioned from their blinded daily dose (placebo, 0.2 mg/kg/day, 0.8 mg/kg/day, or 30 mg/day) to the 0.2 mg/kg dose during the 2-week interval between Visits 12 and 13, without breaking the blind. The IWR system assigned two bottles of IMP to the subject, one for each step in the transition. A new bottle of IMP was started by the subject at each level of the transition step.

Table 3. Transition Algorithm

Dose Group in Double-Blind Study	Transition Step 1 Day 1-4 after Visit 12	Transition Step 2 Days 5-14 after Visit 12
ZX008 0.2 mg/kg/day	ZX008 0.2 mg/kg/day	ZX008 0.2 mg/kg/day
ZX008 0.8 mg/kg/day	ZX008 0.4 mg/kg/day	ZX008 0.2 mg/kg/day
Placebo	ZX008 0.2 mg/kg/day	ZX008 0.2 mg/kg/day
Note: maximum daily dose of ZX008 is 30 mg.		

Subjects who had been randomized to placebo increased their dose to 0.2 mg/kg/day beginning on Day 1 of the transition (the day following Visit 12.) Subjects who had been randomized to 0.2 mg/kg/day continued to receive that dose. Subjects who had been randomized to 0.8 mg/kg/day or were receiving the maximum dose of 30 mg/day decreased to a dose of ZX008 0.4 mg/kg/day, or a maximum of 30 mg/day. After 4 days at this dose level (Day 5), these subjects decreased their dose to 0.2 mg/kg/day. Subjects were to report to the clinic on Day 15 for enrollment into the open-label extension study.

Data from the Taper or Transition period will not be included towards the planned efficacy endpoints except where specified, but will be included in the safety analyses.

**2.8. Study Procedures and Flowchart**

The full list and timing of study procedures is provided in Table 4.

This document is confidential.

**Statistical Analysis Plan**

Sponsor: Zogenix International Limited; Protocol No.: ZX008 Study 2 (ZX008-1501 and ZX008-1502)

Table 4: Schedule of Assessments

Study Assessments	Baseline Period a			Titration + Maintenance Period								EOS/ ET b	Post- Dosing	Cardiac Follow-up
	Screening	2	Random- ization	Titration Period			Maintenance Period							
	1	(Phone)	3	4, 5 (Phone)	6	7 (Phone)	8	9 (Phone)	10	11 (Phone)	12			
Visit Number	1	2 (Phone)	3	4, 5 (Phone)	6	7 (Phone)	8	9 (Phone)	10	11 (Phone)	12	13	14	
Study Day	-42 to -41	-21	-1	1	4, 8	15	29	43	57	71	85	99	113	3-24 mo post dose
Informed Consent (subject and parent)	X													
Inclusion/Exclusion Criteria	X		X											
Demographics	X													
Medical/Neurological History	X													
Epilepsy history	X													
Collect retrospective seizure diary data	X													
Prior Medication	X		X											
Physical Examination, complete	X		X						X			X		X c
Physical Examination, abbreviated					X			X		X				X c
Neurological Examination, complete	X										X			
Neurological Examination, abbreviated			X		X						X			
Vital signs	X		X		X			X		X		X		
Weight, Height, BMI	X		X		X			X		X		X		
12-lead ECG	X		X		X			X		X		X		X c
Doppler ECHO		X						X c				X c		X c
Urine pregnancy test	X c		X c		X c			X c		X c		X c		
Clinical laboratory evaluation (hematology/clinical chemistry/urinalysis, etc)	X		X		X			X		X		X		
Plasma sample for ZX008 pharmacokinetics								4X c						
Plasma sample for background AEDs			X c		X c			X c				X c		
Urine THC Panel/Whole blood CBD	X		X		X			X		X		X		
Janner Staging (for subjects >7 years old)			X		X							X		
Subject Diary	D	R	C/R/D		R	C/R/D	R	C/R/D	R	C/R/D	R	C/R/D d	C/R	
Epilepsy genotype panel	X											X		
Study Medication			D		R e	C/R/D	R	C/R/D	R	C/R/D	R	C/R/D f	C/R	
C-SSRS	X		X			X		X		X		X		

This document is confidential.

**Statistical Analysis Plan**

Sponsor: Zogenix International Limited; Protocol No.: ZX008 Study 2 (ZX008-1501 and ZX008-1502)

Table 4: Schedule of Assessment (Continued)

Study Assessments	Baseline Period a			Titration + Maintenance Period								EOS/ ET b	Post-Dosing	Cardiac Follow-up
	Screening	2 (Phone)	Random- ization	Titration Period			Maintenance Period							
Visit Number	1		3		4, 5 (Phone)	6	7 (Phone)	8	9 (Phone)	10	11 (Phone)	12	13	14
Study Day	-42 to -41	-21	-1	1	4, 8	15	29	43	57	71	85	99	113	3-24 mo post dose
Clinical Global Impression - Improvement (assessed by parent/caregiver)						X		X		X		X		
Clinical Global Impression - Improvement (assessed by principal investigator)						X		X		X		X		
BRIEF			X					X				X		
QOLCE			X					X				X		
PedsQL			X					X				X		
EQ-5D-5L (QoL of parent/caregiver)			X					X				X		
HADS (Affect of parent/caregiver)			X					X				X		
Randomize subject			X											
First Day of Study Drug Administration				X										
Daily Diary Completion							X							
Concomitant Medication									X					
Adverse events							X							
Adverse events of special interest							X							X

AED=antiepileptic drug; BMI=body mass index; BRIEF=Behavior Rating Inventory of Executive Function; C=Colex, CBD=cannabidiol; D=Dispense; ECG=electrocardiogram; EOS=end of study; ET=early termination; EQ-5D-5L=standardized measure of health status; HADS=Hospital Anxiety and Depression Scale; PedsQL=Pediatric Quality of Life Inventory; QoL=quality of life; QOLCE=Quality of Life in Childhood Epilepsy; R=Review

- a: The Baseline Period is comprised of the initial screening for the study and the assessment of baseline seizure activity recorded daily in the diary.
- b: Subjects who are discontinued early and those who complete the study and choose not to enroll in the separate open-label extension will be tapered off study medication over an up to 2-week period.
- c: Follow-up ECG, ECHO, and physical examination if warranted will be performed 3-6 months after early termination, or for those subjects who complete the study but do not enter the open-label extension study
- d: The Visit 8 ECHO must be performed any time between Study Day 40 and Study Day 54. The Visit 12 ECHO must be performed any time between Study Day 90 and Study Day 113; if a subject discontinues early from the study, the ECHO should be scheduled as soon as pract cal. If the Study Day 43 ECHO was completed ≤ 30 days prior to early termination, the Visit 12 ECHO will not be performed provided the parent/guardian agrees to bring the subject to the clinic for the cardiac follow-up visit.
- e: Females of child-bearing potential
- f: Plasma sample for pharmacokinetic assessment will be conducted prior to the dose at Visit 8 and 1, 2, and 4-6 hours after dose administration.
- g: Plasma sample for assessment of background AED(s) will be conducted prior to the dose of AED(s) at Visits 3, 6, 8 and 12.
- h: Study drug/diary dispensed for the Transition Period for subjects entering the open-label extension study and for the Taper Period for subjects exiting the study.
- i: Site personnel will review study medication dosing procedure (titration) with parent/caregiver.
- j: Study drug administration begins in the morning of Study Day 1.
- k: Only adverse events related to cardiac safety will be collected at this visit.
- l: Mandatory one time collection any time during or after screening.

This document is confidential.

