**Taper Period:**

Subjects who complete the Maintenance Period and were not continuing into the open-label extension study and subjects who discontinued from the study early were to be tapered off from study medication. Study medication was administered as equal doses BID in the morning and in the evening approximately 12 hours apart, with food. Each dose should have been separated by a minimum of 8 hours and a maximum of 12 hours. A missed dose of study medication may have been taken later up to 8 hours before the next scheduled dose; otherwise, the missed dose should not be given. IMP was administered using the oral dosing syringe provided.

In order to maintain the blind across all dose groups, all subjects who did not continue into the open-extension study participated in a dose-tapering procedure over the course of 8 days. On the first day of the tapering period subjects in the ZX008 0.8 mg/kg/day group decreased to a dose of ZX008 0.4 mg/kg/day BID (maximum 30mg/day). After 4 days at this dose level (Day 5), subjects randomized to the ZX008 0.8 mg/kg/day group decreased their dose to 0.2 mg/kg/day. Subjects in the ZX008 0.2 mg/kg/day group decreased their dose to placebo on the first day of tapering while doses in the placebo group remained constant throughout the tapering procedure. On Day 9, all subjects stopped taking study medication. The taper was expected to take a total of 8 days (Table 2). A new bottle of IMP was started by the subject at each level of the taper step.

Table 2. Taper Algorithm

Randomized Group	Taper Step 1 Day 1-4 after study completion or early termination	Taper Step 2 Days 5-8 after study completion or early termination

This document is confidential.

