**Statistical Analysis Plan**

Sponsor: Zogenix International Limited; Protocol No.: ZX008 Study 2 (ZX008-1501 and ZX008-1502)

The targeted study day and allowable windows for visits in are reproduced from the protocol below. Early termination visits will be mapped to a visit based on these windows.

Table 5. Time Windows for Assessments

Visit / Procedure	Time window (relative to scheduled visit / procedure)
Visit 1 (Clinic; Study Day -43 to -42 or -42 to -41):	Not applicable
Visit 2 (Phone; Study Day -21)	± 3 days
Visit 3 (Clinic; Study Day -1; Randomization)	+ 4 days a
Visits 4, 5 (Phone: Study Days 4, 8)	± 3 days
Visit 6 (Clinic; Study Day 15)	± 4 days
Visit 7 (Phone: Study Day 29)	± 4 days
Visit 8 (Clinic; Study Day 43)	± 4 days
Visit 9 (Phone: Study Day 57)	± 4 days
Visit 10 (Clinic; Study Day 71)	± 4 days
Visit 11 (Phone: Study Day 85)	± 4 days
Visit 12 (Clinic; Study Day 99)	± 4 days
Visit 13 (Clinic; Study Day 113; post dosing)	± 4 days
Visit 14 (ECHO clinic; 3-6 months after last dose)	+ 30 days
Blood collection for ZX008 PK	± 15 minutes
Blood collection for AED concentration	Prior to morning dose of AED medication

AED=antiepileptic drug (s); ECHO=echocardiogram; PK = pharmacokinetics

a In cases where the screening period is extended beyond 42 days, the immediate 42 days before the Randomization visit will be used to calculate the baseline seizure frequency

This document is confidential.

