### 3.2.3 Collection of Echocardiograms

ECHOs were taken at Screening, Week 6 (Visit 8), and Week 14 (Visit 12). For each ECHO, cardiac technicians check to make sure the Nyquist Limit (color scale) was set between 60 cm/s and 80 cm/s. All sonographers at the study sites submitted a certification ECHO before study ECHOs were obtained.

The time of the ECHO was not controlled.

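### The end-of-study ECHO may be taken after the randomised treatment has been switched, and the cardiovascular SAP has no rule for separating those scans

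*SAP*

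**What the plan says.** **Scan window.** Footnote d to Table 4 of the Study 2 SAP says "The Visit 12 ECHO must be performed any time between Study Day 90 and Study Day 113". Footnote d to Table 1 of the Study 1 SAP carries the same text. After early discontinuation the ECHO is to be arranged promptly, but no latest day is given.

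**Visit date.** Table 5 of the Study 2 SAP lists "Visit 12 (Clinic; Study Day 99" with a tolerance of ± 4 days, and Visit 13 at Day 113.

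**Treatment after Visit 12 (Study 2 SAP, section 2.7).** Extension entrants change dose "during the 2-week interval between Visits 12 and 13":
- "Subjects who had been randomized to placebo increased their dose to 0.2 mg/kg/day beginning on Day 1 of the transition", which section 2.7 defines as the day after Visit 12.
- The 0.2 mg/kg/day arm continues unchanged.
- The 0.8 mg/kg/day arm "decreased to a dose of ZX008 0.4 mg/kg/day, or a maximum of 30 mg/day"; its second step, to 0.2 mg/kg/day, comes on transition Day 5.

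Subjects not entering the extension taper. "Subjects in the ZX008 0.2 mg/kg/day group decreased their dose to placebo on the first day of tapering". The 0.8 arm steps through 0.4 and 0.2 mg/kg/day, the placebo arm stays on placebo, and everyone is off study drug from taper Day 9.

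**Analysis.** Section 3.2.3 of the Study 2 cardiovascular SAP says "ECHOs were taken at Screening, Week 6 (Visit 8), and Week 14 (Visit 12"). Section 4 describes an assessment of up to 14 weeks of dosing, and section 4.2.1 uses all available data. Sections 2.3.2 and 4.5.2 compare the arms by visit and at end of study on mitral and aortic regurgitation, pulmonary artery systolic pressure (PASP) and right ventricular outflow tract acceleration time (RVOT). In the main Study 2 SAP, section 5.2 attributes safety data to the randomised arm and section 6.5 assigns by-visit data to the nominal visit. The cardiovascular SAP sets no different rule and says nothing about scans dated after Visit 12.

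**The concern.** Only two post-baseline ECHOs are scheduled on study, and the Visit 12 scan is the one that follows the full randomised exposure. A reader of the end-of-study tables will take it as a comparison of 14 weeks of ZX008 with 14 weeks of placebo. The permitted window lets some of those scans fall when the randomised contrast in dose has narrowed or gone. A late scan of an extension entrant from the placebo arm is taken on ZX008 but tabulated as a placebo scan. A late scan from the 0.8 arm is taken at a lower dose or off drug.

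For any measure that follows current dose, this pulls the arms together. In a safety comparison that is the less cautious direction. The label gives no warning of it.

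**Working it through.** No sample size was calculated for cardiac safety, so there is no power figure to reproduce. The check is calendar arithmetic and an overlay of the dosing tables.

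**1. The window's upper limit.** Nominal Visit 12 plus the two-week transition is 99 + 14 = Day 113. This equals both Visit 13 and the stated end of the ECHO window, so the window covers the whole nominal taper or transition period.

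**2. Share of permitted days after Visit 12.** Window length: 113 − 90 + 1 = 24 days. Share = (113 − day of Visit 12) / 24.

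| Visit 12 on | Days after it | Share |
|---|---|---|
| Day 95 (earliest in window) | 18 | 75% |
| Day 99 (nominal) | 14 | 58% |
| Day 103 (latest in window) | 10 | 42% |

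**3. Treatment at the time of scan, Visit 12 on Day 99** (ZX008 in mg/kg/day, subject to the 30 mg/day maximum; P = placebo).

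| Day | Extension: placebo / 0.2 / 0.8 arm | Taper: placebo / 0.2 / 0.8 arm |
|---|---|---|
| 90–99 | P / 0.2 / 0.8 | P / 0.2 / 0.8 |
| 100–103 | 0.2 / 0.2 / 0.4 | P / P / 0.4 |
| 104–107 | 0.2 / 0.2 / 0.2 | P / P / 0.2 |
| 108–113 | 0.2 / 0.2 / 0.2 | none / none / none |

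Within either route, the 0.2 arm and placebo receive the same treatment from Day 100. The 0.8 arm and placebo do so from Day 104 on the extension route and from Day 108 on the taper route. By Day 113 an extension entrant from the placebo arm has had 14 days of ZX008.

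**4. Drug remaining on the taper route.** Days 108–113 are 6 drug-free days, or 144 hours. The cardiovascular SAP gives half-lives of about 20 hours (parent) and 30 hours (metabolite). 144/20 = 7.2 half-lives leaves 2^(−7.2) ≈ 0.7%; 144/30 = 4.8 half-lives leaves 2^(−4.8) ≈ 3.6%. This is a simple decay illustration for plasma drug and says nothing about valve structure.

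**5. Possible dilution.** Let f be the fraction of end-of-study scans taken late, equal across arms, and suppose late scans carry no arm difference on a dose-dependent measure. Then the observed contrast = (1 − f) × the on-treatment contrast. The documents do not give f, so it is assumed here: f = 20% retains at most 80% of the contrast lost to nothing else, and f = 50% retains 50%. These are worst cases for each f; if late scans keep part of the difference, more is retained.

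**The case against.** The strongest reply is that including these data is deliberate and disclosed. Section 2.7 of the main SAP puts taper and transition data into the safety analyses, section 10 reports safety over 16 weeks, and the cardiovascular SAP uses everything available. For an uncommon structural harm, dropping scans costs ascertainment. This stands, and it is why the all-scans analysis should be kept. It does not explain the Week 14 label or the 14-week description in the plan that actually governs the ECHO analysis.

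Second, the main ECHO focus is clinically meaningful mitral or aortic regurgitation. The cardiovascular SAP's introduction reports a median of 9 months of drug use (range 1–39) among historical valvulopathy cases. Nothing in the documents suggests that valve change regresses within days of a step-down, or that two weeks at 0.2 mg/kg/day produces it. This also stands. The dilution argument fits PASP and RVOT better, and these are secondary, with RVOT confirmatory only.

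Third, much of the plan does not depend on late scans. Visit 8 ECHOs (Day 40–54) fall within double-blind treatment, and counts based on any post-baseline scan keep a signal seen there. Heat maps and listings show individual subjects. This limits the damage, although an any-post-baseline count can still record a finding made on ZX008 against placebo.

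A reader might infer that every late placebo scan is a scan on ZX008. It is not: placebo subjects who taper stay on placebo. Nor do the percentages above describe scans; they are shares of permitted days.

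**Conclusion.** The point holds as a gap in the cardiovascular SAP. As written, its end-of-study ECHO comparisons can mix scans on randomised treatment with scans after the switch, and can count scans taken on ZX008 as placebo scans. On a nominal schedule 58% of the permitted days are exposed to this, and 42% to 75% across the Visit 12 window. Early-termination scans share the problem without a stated upper limit.

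The size of any bias is unknown, because neither the distribution of scan dates nor the split between extension and taper is given. For measures that track current dose, the bias would be towards no difference. For regurgitation it may be small if cumulative exposure drives the finding. A reader might go further and conclude that the main cardiac-safety analysis conceals harm. The documents do not support that: they show neither how many scans were late nor that valve findings respond to short dose changes. This is a worthwhile, inexpensive improvement to the analysis plan and does not invalidate it.

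**What to change.** Leave the scan schedule and dosing as they are, and amend sections 2.3.2 and 4.5.2 of the cardiovascular SAP:

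- Classify each end-of-study or early-termination ECHO by its actual date relative to the last randomised titration-plus-maintenance dose.
- Keep the all-scans analysis for ascertainment.
- Add a pre-specified comparison of mitral and aortic regurgitation, PASP and RVOT restricted to scans up to that dose.
- List later scans separately by route (taper or transition), with the treatment at the time of scan and the days since the last randomised dose.
- Reconcile the Week 14 label and the 14-week description with footnote d and Table 5.

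The cost is a few sentences of SAP text and one date comparison per scan. The downside is a smaller n in the added on-treatment table; no subject is lost from the all-scans analysis.

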**Statistical Analysis Plan**

Sponsor: Zogenix International Limited; Protocol No.: ZX008 Study 2 (ZX008-1501 and ZX008-1502)

The targeted study day and allowable windows for visits in are reproduced from the protocol below. Early termination visits will be mapped to a visit based on these windows.

Table 5. Time Windows for Assessments

Visit / Procedure	Time window (relative to scheduled visit / procedure)
Visit 1 (Clinic; Study Day -43 to -42 or -42 to -41):	Not applicable
Visit 2 (Phone; Study Day -21)	± 3 days
Visit 3 (Clinic; Study Day -1; Randomization)	+ 4 days a
Visits 4, 5 (Phone: Study Days 4, 8)	± 3 days
Visit 6 (Clinic; Study Day 15)	± 4 days
Visit 7 (Phone: Study Day 29)	± 4 days
Visit 8 (Clinic; Study Day 43)	± 4 days
Visit 9 (Phone: Study Day 57)	± 4 days
Visit 10 (Clinic; Study Day 71)	± 4 days
Visit 11 (Phone: Study Day 85)	± 4 days
Visit 12 (Clinic; Study Day 99)	± 4 days
Visit 13 (Clinic; Study Day 113; post dosing)	± 4 days
Visit 14 (ECHO clinic; 3-6 months after last dose)	+ 30 days
Blood collection for ZX008 PK	± 15 minutes
Blood collection for AED concentration	Prior to morning dose of AED medication

AED=antiepileptic drug (s); ECHO=echocardiogram; PK = pharmacokinetics

a In cases where the screening period is extended beyond 42 days, the immediate 42 days before the Randomization visit will be used to calculate the baseline seizure frequency

This document is confidential.

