**6.5. Visit Windows**

The following rules will be used to window data into treatment periods for by treatment period tabulations. For all by-visit tabulations, the nominal visit as recorded on the CRF will be used.

Double Blind Treatment Period	
The Double-Blind Treatment Period start date is the date of first treatment, Study Day 1 (ie, the day after V3). The Double-Blind Treatment Period end date is the last date the patient was on study treatment.
 
The Double-Blind Treatment Period consists of 16 weeks from first treatment start date, which includes 2 weeks of Titration period, 12 weeks of Maintenance period and 2 weeks of Taper/Transition period; therefore the end date would be considered the date at Visit 13.
 
For subjects who discontinue early from the study, the double-blind treatment period end date will be the date at the early termination visit (Visit 12).

Titration Period	
The Titration Period covers the first 14 ± 4 days of treatment while subjects are titrated to their randomized dose. It begins on the first day of treatment (Study Day 1) and extends through Visit 6 (when the patient has reached their randomization dose). The Titration Period applies to all subjects including placebo recipients. If a subject withdraws from the study prior to treatment in the maintenance period, all safety assessments and events up to and including the date of study withdrawal will be tabulated in the titration period.

Maintenance Period	
The Maintenance Period covers the 12 weeks following the end of the titration period. It begins on the date of Visit 6 + 1 day and extends through the end of study/early termination visit (Visit 12).

Titration + Maintenance Period (T+M)	
The T+M period combines the Titration and Maintenance periods, beginning on the date of first treatment (Study Day 1) and extending to the end of study/end of treatment visit. The T+M period is considered the treatment period.

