### Clinical Global Impression – Improvement Rating, as assessed by the Parent/Caregiver

The parent/caregiver and the investigator will rate their global impression of the subject's condition at each clinic visit after randomization: end of Titration period (Visit 6), Maintenance period (Visit 8 and 10), and at End of study (Visit 12).

The CGI-I scale measures the change in the subject's clinical status from a specific point in time, i.e., the Baseline Period. The CGI-I rating scale permits a global evaluation of the subject's improvement over time. The severity of a patient's condition is rated on a 7-point scale ranging from 1 (very much improved) to 7 (very much worse) as follows:

- 1=very much improved
- 2=much improved
- 3=minimally improved
- 4=no change
- 5=minimally worse
- 6=much worse
- 7=very much worse

The mean (SD) CGI-I score, and the number and percentage of subjects who showed improvement (i.e., had a score of 3 or lower), and the number and percentage who did not improve (i.e., had a score of 4 or higher) will be presented for each for each treatment group at each assessment timepoint. Each assessment time point will also include a comparison between each active treatment and the placebo group using the Cochran-Mantel-Haenszel test stratified by age group, and a frequency distribution of the

This document is confidential.

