#### 3.1.3 Collection of ECGs

The clinical ECG database will be derived from 12-lead ECGs collected from the ELI-150c ECG machines.

Single, 12-lead ECGs were collected at Screening, Baseline (Visit 3), Week 6 (Visit 8), and Week 14 (Visit 12). ECGs were collected after the subjects had been in supine position resting for  $\geq 5$  minutes.

The time of the ECG was not controlled.

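### The Study 2 SAP has two unreconciled rules for placing early-termination visits, and the windows used by one of them cannot place most early-termination clinic assessments

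*SAP*

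**What the plan says.** Section 2.8 of the Study 2 SAP introduces Table 5 as target days and allowable windows taken over from the protocol, and adds: "Early termination visits will be mapped to a visit based on these windows". The table lists clinic and phone visits together, with tolerances of 3 days for Visits 4 and 5 and 4 days for Visits 6 to 13.

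Section 6.5 gives a different convention: "For all by-visit tabulations, the nominal visit as recorded on the CRF will be used". It makes no exception for early termination. For subjects who stop early it says that "the double-blind treatment period end date will be the date at the early termination visit (Visit 12"), and the schedule in Table 4 heads the Visit 12 column EOS/ET.

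Section 8.2.2 has CGI-I rated at Visits 6, 8, 10 and 12 only, and tests it by visit: "Each assessment time point will also include a comparison between each active treatment and the placebo group using the Cochran-Mantel-Haenszel test stratified by age group". Sections 10.4 and 10.5 summarise laboratory values, vital signs and weight over the on-study visits. The Study 1 SAP (section 6.1.6) has the nominal-visit rule but no mapping sentence.

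**The concern.** The two rules build different data sets. A rating taken at an ET visit on Day 50 goes into the Visit 12 test under section 6.5. Under section 2.8 it goes wherever Table 5 puts Day 50, which is nowhere. Two programmers following the same SAP could therefore produce different Visit 12 CGI-I results.

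Subjects who leave early may well be those who did not improve or did not tolerate treatment. If dropout differs by arm, the by-visit contrast depends on which rule is used. Section 6.4 itself notes that differential dropout leading to missing assessments can affect inference, though it says so about the primary endpoint.

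**Working it through.** **Inputs.** Target days and tolerances come from Table 5, CGI-I visits from section 8.2.2, and dropout in Study 1 (9/119) from section 6.4. The day of early termination is not given, so its distribution is an assumption.

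**The plan's own figure.** 9/119 = 7.56%, as stated.

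**Windows** (target day minus and plus tolerance):

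| Visit | Type | Days |
|---|---|---|
| 4 | phone | 1–7 |
| 5 | phone | 5–11 |
| 6 | clinic | 11–19 |
| 7 | phone | 25–33 |
| 8 | clinic | 39–47 |
| 9 | phone | 53–61 |
| 10 | clinic | 67–75 |
| 11 | phone | 81–89 |
| 12 | clinic | 95–103 |

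**Count of Days 1–94**, before the Visit 12 window opens:
- Clinic window: 11–19, 39–47, 67–75 = 3 × 9 = 27 days (28.7%).
- Phone window only: 1–10, 25–33, 53–61, 81–89 = 10 + 3 × 9 = 37 days (39.4%).
- No window: 20–24, 34–38, 48–52, 62–66, 76–80, 90–94 = 6 × 5 = 30 days (31.9%).
- Two windows: Days 5–7 (Visits 4 and 5) and Day 11 (Visits 5 and 6; counted above as clinic).

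**Share of ET days that reach no clinic-visit row under section 2.8:**
- Even over Days 1–94: (37 + 30)/94 = 71.3%.
- Days 1–47 only: (19 + 10)/47 = 61.7%.
- Days 48–94 only: (18 + 20)/47 = 80.9%.
- Linear weighting to early days 68.6%, to late days 74.0%.

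Under section 6.5, all ET values enter Visit 12, whatever their day.

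**Number of subjects.** 0.0756 × 120 = 9.1, about 9 in all and about 3 per arm. With even timing, the 9 split as 9 × 30/94 = 2.9 in gaps, 9 × 37/94 = 3.5 on phone visits and 9 × 27/94 = 2.6 on clinic visits.

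**Effect on one Visit 12 CGI-I rate.** Assume 24 of 40 in an arm improve, 3 are unimproved dropouts before Day 95, and everyone else is rated at Visit 12. Section 6.5 gives 24/40 = 60%. Section 2.8 gives 24/37 = 65%.

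**The case against.** The strongest reply is that section 2.8 speaks of ET visits specifically and section 6.5 states the general convention, so the specific sentence governs. That is an ordinary reading, though the SAP does not say so. It settles the contradiction but not the second problem: the governing rule would then rest on windows that leave gaps, overlap, and include phone visits at which CGI-I is not scheduled.

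A reader might infer that most dropouts' last data are lost or unusable. The document does not support that. It has no rule for an ET visit that falls in no window, and the values would still appear in listings. What can be said is that the rule gives them no by-visit clinic row. QOLCE, PedsQL, HADS and BRIEF changes, and the EQ-5D-5L VAS change, are defined at End of Study/ET and need no window. C-SSRS results count any event during T+M, and adverse events are summarised by period. The primary and key secondary endpoints come from diary data over T+M.

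A reader might also infer that section 6.5 passes off early values as Week 14 data. The main Study 2 SAP labels the Visit 12 column EOS/ET. The wording "Week 6 (Visit 8), and Week 14 (Visit 12") stands in section 3.1.3 of the separate cardiovascular SAP and concerns ECGs.

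Finally, the 60% versus 65% contrast measures the disagreement between the two rules at Visit 12, not the harm from the gaps. Any rule based on study day takes early ET ratings out of Visit 12. That objection stands, and it shapes the fix.

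**Conclusion.** The concern holds in limited form. The SAP has two ET rules with no stated precedence, and the windows named in section 2.8 cannot place most ET clinic assessments. The count of 67 of 94 days follows from Table 5. Reading it as 71% of ET visits assumes even timing, but it stays a majority (62% to 81%) in every timing tried.

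The consequence is modest: by-visit CGI-I tests, which are additional secondary endpoints outside the six-step hierarchy of section 6.3, and by-visit vital-sign, weight and laboratory tables. About 9 of 120 subjects would be involved if Study 2 dropout matches Study 1. The 5-point shift in one arm's Visit 12 CGI-I rate is an illustration with assumed numbers. A reader might take it as bias in the trial's main conclusions, but those do not use these visits. The rule should still be corrected, because it decides which data enter a planned test.

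**What to change.** Before unblinding:
- Replace the mapping sentence in section 2.8 with contiguous analysis windows for ET visits, clinic visits only, cut at the midpoints (15 + 43)/2 = 29, (43 + 71)/2 = 57 and (71 + 99)/2 = 85: Visit 6 Days 1–29, Visit 8 Days 30–57, Visit 10 Days 58–85, Visit 12 Day 86 to the last T+M day. No day is then unassigned or placed on a phone visit.
- State that an on-schedule value is kept over an ET value in the same window. Otherwise the latest-value rule in section 6.1 would let the ET value replace it.
- Keep ET values as EOS/ET for endpoints defined that way.
- Amend section 6.5 so that the nominal visit is used except for ET visits.
- Add a supportive CGI-I analysis at EOS/ET, using the last on-treatment rating.

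The cost is SAP wording and a small programming change. Some ET values are grouped up to 14 days from the target day, and the earliest ones join the end-of-titration visit. ET ratings before Day 86 (85 of 94 days, 90%) still do not contribute to the Visit 12 test. In the illustration above, with even timing, the rate would be 24/(37 + 3 × 9/94) = 24/37.3 = 64%, which is why the EOS/ET analysis is needed alongside.
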